Objectives	
The objective of this clinical investigation is to demonstrate the safety and efficacy/performance of the ReUnion RSA System.
 
Efficacy/performance of the procedure will be measured the American Shoulder and Elbow Surgeons (ASES) Shoulder Score.
 
Safety of the ReUnion RSA System will be demonstrated through reporting of device-related intra-operative and post-operative Adverse Events (AEs).

Target Population	80 subjects are to be enrolled in this clinical investigation. Enrolled subjects will be assessed at Pre-Operative, Operative/Discharge, and at 6 Weeks, 6 Months, 12 Months, 24 Months and annually thereafter up to 10 years following the index procedure.

Endpoints	
Primary Endpoint:
 
The objective of the clinical investigation is to demonstrate the efficacy/performance of the device at 24 months, as measured by the ASES Shoulder Score.
 
Secondary Endpoints:
 
• Safety: Incidence of device-related intra-operative and post-operative AEs• Efficacy/Performance: Implant survivorship will be monitored
Inclusion Criteria:	
a. Subject is willing to sign the informed consent.b. Subject is willing and able to comply with post-operative scheduled clinical assessments.c. Subject is male or non-pregnant female and 18 years or older at the time of surgery.d. Subject's joint has gross rotator cuff deficiency, a functional deltoid muscle and is anatomically and structurally suited to receive the implant and subject has one or more of the following:
• Painful, disabling joint disease of the shoulder resulting from degenerative arthritis or rheumatoid arthritis• Failed previous shoulder joint replacement
Exclusion Criteria:	
a. Subject has an active or suspected latent infection in or about the shoulder joint.b. Subject has mental or neuromuscular disorder which would create an unacceptable risk of prosthesis instability, prosthesis fixation failure or complications in postoperative care.c. Subject has bone stock compromised by disease, infection or prior implantation which cannot provide adequate support and/or fixation to the prosthesis.d. Subject has anticipated activities which would impose high stresses on the prosthesis and its fixation.e. Subject is obese such that he/she produces a load on the prosthesis which can lead to failure of fixation of the device or to failure of the device itself.f. Subject has concomitant disease(s) which may significantly affect the clinical outcome.g. Subject has traumatic or pathologic fracture of the proximal humerus.

3. General Information and Administrative Structure

3.3. EDC SYSTEM

Name: IBM Clinical Development
Email: [contact]
[contact]

4. Product Information

All components of the ReUnion RSA System have been cleared and approved for sale and use in the United States prior to starting the clinical investigation. 510(k) Clearance was received on 27Dec2013. This system is to be used only for indications for which it has been approved. Please see the approved Instructions for Use (IFU) and Operative Technique manuals for a detailed description of the medical device(s) and instrumentation as well as the intended use information.

Medical device product traceability will be achieved by capturing the implant lot number.

5. Risks and Benefits

This prospective, multicenter clinical investigation is designed to examine the safety and efficacy/performance of the ReUnion RSA System in accordance with the approved IFU, labelling and instrumentation. The potential risks to subjects are described in the approved IFU and Operative Technique manuals.

Potential benefits resulting for the ReUnion RSA System over other devices and procedures as demonstrated by superior scoring on the outcome survey and positive results on other clinical evaluation measurements would suggest affirmative clinical efficacy.

6. Introduction

The ReUnion RSA System is designed as a reverse total shoulder endoprosthesis to address unrepairable gross rotator cuff tear, rotator cuff arthropathy with pseudoparalysis of the shoulder joint, advanced arthritic and rheumatic disorders affecting the shoulder joint, and failed previous shoulder arthroplasty. The ReUnion RSA System is comprised of a Humeral Cup, Humeral Insert, Glenosphere, Glenoid Baseplate and Screws. It is used with the humeral stems from the ReUnion Total Shoulder Arthroplasty (TSA) System. The intended purposes of the ReUnion RSA System are to achieve pain relief, improvement of range of motion and restoration or improvement of the shoulder function while ensuring long-term replacement of the shoulder joint with sufficient stability of all endoprosthesis components.

7. Clinical Investigation Design

This investigation is a prospective, multicenter clinical investigation. It is anticipated that a total of eighty (80) subjects will be enrolled at approximately 4-7 sites. Neither subjects nor investigators are blinded to treatment and the clinical investigation does not include a contemporaneous control. The clinical investigation has been designed to follow the surgeon's standard of care for joint arthroplasty subjects, which entails clinical evaluation on a regular ongoing basis, or as needed should the subject become symptomatic in the treated joint. The enrollment period is expected to occur over 12 months.

7.1. CLINICAL INVESTIGATION RATIONALE

This clinical investigation will evaluate the safety and efficacy/performance of the ReUnion RSA System.

8. Objective

8.1. PRIMARY ENDPOINT

The primary endpoint of the clinical investigation is to demonstrate non-inferiority of the device to the selected literature controls, as measured by the ASES Shoulder Score at 24 Months post-operative.

8.2. SECONDARY ENDPOINT

In addition to the principal endpoint, information on the following outcomes will be assessed up to 10 years after the index procedure:

Safety: Incidence of device-related intra-operative and post-operative AEs

Efficacy/Performance: Implant survivorship will be monitored

9. Selection of Clinical Investigation Population

Subjects participating in this clinical investigation will be recruited from the investigator's standard subject population, where all patients presenting for primary or revision total shoulder replacement will be evaluated for clinical investigation participation based on the eligibility criteria listed below.

9.1. INCLUSION CRITERIA

- a. Subject is willing to sign the informed consent.
- b. Subject is willing and able to comply with postoperative scheduled clinical and radiographic evaluations.
- c. Subject is male or non-pregnant female and 18 years or older at the time of surgery.
- d. Subject's joint has gross rotator cuff deficiency, a functional deltoid muscle and is anatomically and structurally suited to receive the implant and subject has one or more of the following:
 - Painful, disabling joint disease of the shoulder resulting from degenerative arthritis or rheumatoid arthritis
 - Failed previous shoulder joint replacement

9.2. EXCLUSION CRITERIA

- a. Subject has an active or suspected latent infection in or about the shoulder joint.

- b. Subject has mental or neuromuscular disorder which would create an unacceptable risk of prosthesis instability, prosthesis fixation failure or complications in postoperative care.
- c. Subject has bone stock compromised by disease, infection or prior implantation which cannot provide adequate support and/or fixation to the prosthesis.
- d. Subject has anticipated activities which would impose high stresses on the prosthesis and its fixation.
- e. Subject is obese such that he/she produces a load on the prosthesis which can lead to failure of fixation of the device or to failure of the device itself.
- f. Subject has concomitant disease(s) which may significantly affect the clinical outcome.
- g. Subject has traumatic or pathologic fracture of the proximal humerus.

9.3. WITHDRAWAL CRITERIA

If during the clinical investigation a subject must be withdrawn prematurely, then the procedures outlined in this section must be followed. These procedures should not interfere with the initiation of any new treatments that are necessary to treat a subject's condition. Information on all withdrawn subjects will be documented.

Subjects may be withdrawn from the clinical investigation for any of the following reasons:

- a. Subject Withdrawal: A subject may voluntarily withdraw from the clinical investigation at any time and for any reason. The subject should be asked when possible, and without any form of coercion, the reason for his/her decision. If the participant withdraws from the clinical investigation completely, then data collected up until the point of withdrawal will be included in the final analysis.
- b. Lost to Follow-Up (LTFU): A subject will be considered LTFU after all reasonable efforts have been made to contact the subject and request his/her continued participation in the clinical investigation. All attempts to contact the subject must be documented and should include at least two attempts to contact the subject by phone and one attempt via a certified letter. Data collected up until the point where the subject is LTFU will be included in the final analysis.
- c. Removal of Device or AE/Incident: The discontinuation of a subject's participation in the clinical investigation due to the removal of the ReUnion RSA System or AE/incident that prohibits his/her continued participation must be fully explained. All available information concerning the removal of the device or AE/incident should be provided. Data collected up until the point of removal or AE/incident will be included in the final analysis.
- d. Death: The discontinuation of a subject's participation in the clinical investigation due to death must be fully explained. All available information concerning the death or AE should be provided. Removal of a subject from continued follow-up in the clinical investigation due to death will not be considered a device failure unless the death is directly caused by, or attributable to, the ReUnion RSA System. Data collected up until the point of death will be included in the final analysis.
- e. Other: A subject may be withdrawn by the investigator if he/she believes it is in the best interest of the subject, or if it is determined by the IRB that a subject's continued participation in the clinical investigation represents an unacceptable risk to the subject. The Sponsor must be notified immediately if this occurs. All data collected up until the point of withdrawal or IRB determination will be included in the final analysis.

A subject may also be withdrawn if the subject is non-compliant with the clinical investigation procedures or visits, or if a selection criteria violation is noted after the subject received the clinical investigation treatment and it is determined that the subject should be discontinued. All data collected up until the point of withdrawal will be included in the final analysis.

10. Clinical Investigation Evaluations, Procedures and Assessments

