10.4. SCHEDULE OF EVENTS

Assessment	Pre-Operative	Operative/ Discharge	6 Weeks ^{a, b} (+/- 2 weeks)	6 Months ^{a, b} (+/- 3 weeks)	12 Months ^{a, b} (+/- 4 weeks)	24 Months ^{a, b} (+/- 4 weeks)	Annually ^b
Informed Consent	X						
Demographics & Medical History	X						
Inclusion/Exclusion	X						
Physical Exam	X		X ^c	X ^c	X ^c	X ^c	X ^c
Surgical Procedure		X					
ASES Shoulder Score	X		X ^d	X ^d	X ^d	X ^d	X ^d
Image Evaluation ^{e, f}	X	X	X	X	X	X	X
Subject Disposition ^g			X	X	X	X	X
	Device-Related AEs/Incidents & Reoperations will be collected throughout the course of the clinical investigation.						

	
a. Follow-up visit schedule to reflect Institutions' Standard of Care practicesb. If the subject misses a visit and is outside of the visit window, then every effort should be made to collect data instead of noting visit as missed.c. Evaluation may be collected when subject presents in-clinic for study visit.d. Evaluation can be collected via phone.e. Radiograph collection should follow Institution's Standard of Care practices and no additional x-rays should be made for study purposes.f. CT scans may be collected if part of Institution's Standard of Care practices.g. Subject Disposition assessment will occur at any time point for subject withdrawal prior to the completion of the clinical investigation.
--	-----------------------------------------------------------------------------------------------------------------------------------------------------------------------------------------------------------------------------------------------------------------------------------------------------------------------------------------------------------------------------------------------------------------------------------------------------------------------------------------------------------------------------------------------------------------------------------------------------------------------------------------------------------------------------------------------------------------------------------------------------------------------------------------------------------------------------------------------

Table 1: Schedule of Events

11. Statistical Methods

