11.3.2. Primary Analysis / Endpoint

The objective of the clinical investigation is to demonstrate the non-inferiority (equal or better) of the ASES Shoulder Score in relationship to the officially cleared indications in comparison to respective clinical outcome data in the scientific literature.

[figure not shown]
Data collection of ASES Shoulder Score will start pre-operatively and will be collected according to schedule in Table 1. This will be repeated annually in all subjects who have the prosthesis with full or partial implant survival (including all subjects without removal of all endo-prosthesis components).

The 24 months post-operative results for subjects implanted with ReUnion RSA System will be compared to a historical group and results reported by respective clinical outcome data in the scientific literature. The benchmark sources and values will serve as the control group for the ReUnion RSA System subjects.

Higher ASES Shoulder Score results are linked to better subject results and vice versa.

The clinical investigation endpoint is non-inferiority to the control, meaning the clinical investigation result should be equal or better than the control. In this clinical investigation, an equal or better ASES score result means equal or more (\geq). As only results from samples will be captured, results are mostly estimates of the true population parameter. These estimates vary by a certain area, where it is expected that the true population parameter falls within. Based on this, it is required to specify a lower limit for the acceptable difference or zone of indifference, denoted as $-\theta$.

Hypotheses are developed to allow for a comparison of the 24 months post-operative ASES score effectiveness / performance between the two underlying populations. The 24 months post-operative ASES Shoulder Score is the primary endpoint of this clinical investigation. Hypothesis tests will be one-sided with a significance level α of 5%.

Hypothesis	Equations	Interpretation
Null (H_0)	$A - B < -\theta$	Central tendency of A is inferior to the central tendency of B.
	ReUnion RSA System – Control (Benchmark) $< -\theta$	
Alternative (H_1)	$A - B \geq -\theta$	Central tendency of A is non-inferior to the central tendency of B.
	ReUnion RSA System – Control (Benchmark) $\geq -\theta$	
		
Possible Evidence (p)	Possible Decisions	Possible Conclusions – ASES score

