11.4. MISSING DATA / SAP DEVIATIONS

The intent is to collect as complete a dataset as possible. Nevertheless, in some situations missing data cannot be avoided. The reports and tables therefore will show the number and percentage of missing cases for each analyzed variable in relation to the enrolled cases for each post-operative assessment.

Any deviations from the SAP will be listed in the annual or final reports.

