### 3.1.1. Primary Analysis / Endpoint

The objective of the clinical investigation is to demonstrate the non-inferiority (equal or better) of the ASES Shoulder Score in relationship to the officially cleared indications in comparison to respective clinical outcome data in the scientific literature.

[figure not shown]
Data collection of ASES Shoulder Score will start pre-operatively and will be collected according to schedule in Table 4.4. This will be repeated annually in all subjects who have the prosthesis with full or partial implant survival (including all subjects without removal of all endo-prosthesis components).

The 24 months post-operative results for subjects implanted with ReUnion RSA System will be compared to a historical group and results reported by respective clinical outcome data in the scientific literature. The benchmark sources and values will serve as the control group for the ReUnion RSA System subjects.

Higher ASES Shoulder Score results are linked to better subject results and vice versa.

The clinical investigation endpoint is non-inferiority to the control, meaning the clinical investigation result should be equal or better than the control. In this clinical investigation, an equal or better ASES score result means equal or more ( $\geq$ ). As only results from samples will be captured, results are mostly estimates of the true population parameter. These estimates vary by a certain area, where it is expected that the true population parameter falls within. Based on this, it is required to specify a lower limit for the acceptable difference or zone of indifference, denoted as  $-\theta$ .

Hypotheses are developed to allow for a comparison of the 24 months post-operative ASES score effectiveness / performance between the two underlying populations. The 24 months postoperative ASES Shoulder Score is the primary endpoint of this clinical investigation. Hypothesis tests will be one-sided with a significance level  $\alpha$  of 5%.

Hypothesis	Equations	Interpretation
Null ( $H_0$ )	$A - B < -\theta$	Central tendency of A is inferior to the central tendency of B.
	ReUnion RSA System – Control (Benchmark) $< -\theta$	
Alternative ( $H_1$ )	$A - B \geq -\theta$	Central tendency of A is non-inferior to the central tendency of B.
	ReUnion RSA System – Control (Benchmark) $\geq -\theta$	
		

Possible Evidence (p)	Possible Decisions	Possible Conclusions – ASES score

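### A subject whose implant is completely removed before 24 months can be left without a primary ASES score, and no rule says how that subject enters the primary test

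*Protocol*

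**What the plan says.** Protocol 9.3 opens permissively: "Subjects may be withdrawn from the clinical investigation for any of the following reasons". Reason (c) concerns "The discontinuation of a subject's participation in the clinical investigation due to the removal of the ReUnion RSA System or AE/incident". The sentence goes on to limit the adverse-event part to events that stop the subject from taking part. On data use it says: "Data collected up until the point of removal or AE/incident will be included in the final analysis".

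The primary endpoint is non-inferiority to literature controls, "as measured by the ASES Shoulder Score at 24 Months post-operative" (Protocol 8.1). On collection of the score, Protocol 11.3.2 first refers to the visit schedule and then adds: "This will be repeated annually in all subjects who have the prosthesis with full or partial implant survival". SAP 3.1.1 repeats this and spells out the group as "including all subjects without removal of all endo-prosthesis components". Partial removals therefore stay in, and complete removals fall outside. Footnote d of the schedule (Protocol 10.4, SAP 4.4) says of the post-operative ASES: "Evaluation can be collected via phone".

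On missing values, Protocol 11.4 offers only counts: "The reports and tables therefore will show the number and percentage of missing cases for each analyzed variable". SAP 4.6 says the same. The primary analysis (Protocol 11.3.2, SAP 3.1.1 and 6.6) is a one-sample t-test or sign test of the 24-month scores against 51.87.

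**The concern.** The target of the primary analysis is the 24-month result in subjects implanted with the system. If a subject is explanted and then withdrawn, the score is missing because the device failed. A test on the available scores then describes subjects whose implant survived, which is a narrower and probably more favourable group. There is no concurrent control arm in which the same selection would operate.

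Three parts of the plan might have closed the gap, but none does:

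- The missing-data sections count missing cases without assigning a value or requiring a sensitivity analysis.
- The ITT definition (Protocol 11.2, SAP 5.1) settles who belongs to the set, not what value an unscored member receives.
- The death clause in Protocol 9.3(d) mentions device failure, but no analysis rule says how a failure counts.

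Follow-up after removal is also at stake. Mortality times for subjects not known to have died end at the most recent visit (SAP 6.7.2), so a death after withdrawal can go unrecorded. The same applies to later device-related events and further reoperations.

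**Working it through.** **Inputs from the documents** (Protocol 11.1 and 11.3.2, SAP 3.1.1 and 3.2): planned mean 71.27, SD 19.40, test limit 51.87, alpha 0.05, enrolment 80, drop-out 56%. The drop-out figure leaves 80 × 0.44 = 35 assessable subjects. The sample-size table uses two tails and the analysis section one; the analysis rule (one-sided) is used below, except when reproducing the stated power.

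**The plan's own figure.** One-sample t-test, n = 10, noncentrality (71.27 − 51.87)/19.40 × √10 = 3.162, 9 degrees of freedom, two-sided 5%: power 80.31%, against the stated 80.3%. The inputs are reproduced.

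**Assumptions, not in the documents.** Let f be the share with complete removal and no score at 24 months, s the score these subjects would have had, and m the mean of the others. The ranges used are f = 2.5% to 10% and s = 0 to 40.

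**Inflation of the mean.** m − [(1 − f)m + f·s] = f(m − s). With m = 71.27:

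| f | s = 0 | s = 20 | s = 40 |
|---|---|---|---|
| 2.5% | 1.78 | 1.28 | 0.78 |
| 5% | 3.56 | 2.56 | 1.56 |
| 10% | 7.13 | 5.13 | 3.13 |

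**Passing value** (smallest observed mean that rejects, one-sided t, SD 19.40):

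- n = 80: 51.87 + 1.664 × 19.40/√80 = 55.5
- n = 35: 51.87 + 1.691 × 19.40/√35 = 57.4

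**Does the result change at the planned mean?** Take the worst corner, f = 10% and s = 0. The whole-group mean is 0.90 × 71.27 = 64.1. The zeros also widen the spread: SD = √(0.90 × 19.40² + 0.10 × 0.90 × 71.27²) = 28.2. The passing value at n = 35 becomes 51.87 + 1.691 × 28.2/√35 = 59.9. The expected mean of 64.1 still clears it. For the whole-group mean to fall to 51.87 itself, the removed share would have to be (71.27 − 51.87)/(71.27 − s): 27% for s = 0, 38% for s = 20, 62% for s = 40.

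**Does it matter at the limit?** Set the true whole-group mean to exactly 51.87. The mean of the scored subjects is then (51.87 − f·s)/(1 − f); for f = 5% and s = 20 it is 50.87/0.95 = 53.55. The chance that a nominal 5% one-sided t-test on scored subjects alone declares non-inferiority is shown below, first for s = 40 and then for s = 0:

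| f | 35 subjects before exclusion | 80 subjects before exclusion |
|---|---|---|
| 2.5% | 6% to 10% | 7% to 15% |
| 5% | 7% to 20% | 9% to 33% |
| 10% | 10% to 50% | 14% to 80% |

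**Safety data.** The operation that removes the device is tabulated by type and reason (SAP 6.1). If it is the subject's first reoperation, it is an event in the Kaplan-Meier analysis of SAP 6.7.3. The device-related event behind it counts in the first-event analysis of SAP 6.6 if it is the first. First-event analyses need no data after the event. What can be lost is what follows: later device-related events, further reoperations and vital status.

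**The case against.** The case for leaving the plan alone has substance, and it rules out several stronger readings that a reader might infer.

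- *Every explanted subject is withdrawn, or any adverse event ends participation.* The wording is permissive, and the adverse-event part covers only events that prevent continuation. A site could keep an explanted subject in follow-up. What stands is that inclusion of device failures is left to site discretion.
- *ASES is collected only while the implant is in place.* The implant-survival sentence speaks of yearly repetition, and the schedule gives the 24-month visit its own column. Whether the sentence governs that visit is unclear. Withdrawal under 9.3(c) before 24 months leads to the same loss.
- *The safety conclusions are too favourable.* The documents do not support this, because the removal itself is recorded and analysed. Only information after withdrawal is exposed.
- *The result is biased in every case.* Bias requires at least one complete removal without a score, and a lower score in such subjects. The second is plausible but assumed. The comparison with 71.27 also depends on how the benchmark studies treated explanted patients, which cannot be seen here. If they too scored only retained implants, that comparison is closer to like with like.

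Scoring function while the implant is in place and reporting survivorship separately is also a defensible choice for a device study. Scores after removal may reflect a revision implant, so putting them into the primary test could credit this device with another's result. That argues for sensitivity analyses rather than a changed primary test. It does not remove the need to say which quantity the primary mean estimates.

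**Conclusion.** The gap is real but bounded. The plan permits an explanted subject to leave without a 24-month ASES and has no rule for how that subject enters the primary test, so the reported mean can be conditional on implant survival. On assumed removal shares of 2.5% to 10% and assumed scores of 0 to 40, the mean would be about 0.8 to 7.1 points too high. With a true mean near 71.27, non-inferiority would still be expected, because the limit lies 19.40 points lower. The omission can decide the outcome only if the observed mean is close to the passing value, and it affects the reported mean wherever such subjects exist and score lower. For safety, the loss is confined to events and vital status after withdrawal.

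**What to change.** Amend Protocol 9.3(c) and 11.3.2 and SAP 3.1.1 to state that device removal does not by itself end study follow-up. Unless consent is withdrawn, continue to collect the 24-month ASES (by phone where necessary), device-related events, reoperations and vital status.

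Report the number of subjects with complete removal before 24 months beside the primary result, and prespecify two sensitivity analyses of the primary test:

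1. include the observed post-removal scores;
2. enter every subject with complete removal at a value certain to fail, for example 0, or the lower of the pre-operative score and a fixed value below 51.87. The pre-operative score alone will not do, since nothing keeps it below the limit.

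State which test each analysis uses. Zeros may lead the normality check to select the sign test, in which every value below 51.87 counts alike; in the t-test the chosen value matters.

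The cost is a short protocol amendment with matching SAP text and a few phone calls. The sensitivity means may be less favourable, and some post-removal scores will reflect a revision implant. The collection rule is the urgent part, because scores not collected at 24 months cannot be recovered.

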10.3. FOLLOW-UP EVALUATIONS

Subjects in this clinical investigation will be evaluated at Pre-Operative, Operative/Discharge, and at 6 Weeks (4 weeks – 8 weeks), 6 Months (23 weeks – 29 weeks), 12 Months (48 weeks- 56 weeks), 24 Months (100 weeks – 108 weeks) and annually thereafter. The follow-up evaluations will include assessment of device-related AEs/incidents, radiographs and ASES Shoulder Score.

Investigative site personnel will contact subjects prior to their scheduled follow-up evaluations to encourage compliance with clinical investigation visits and participation.

If a subject misses a visit and is outside of the visit window, then every effort should be made to collect data instead of noting the visit as missed.

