11.2. ANALYSIS POPULATIONS

It is expected during this clinical investigation only one population for ReUnion RSA System will exist and all subjects will be analyzed “Per Protocol” (PP). However, it cannot be fully avoided that in theory subjects might need to be excluded from the PP population. In this occasion, there will be two groups being fully analyzed to ensure transparency and avoid bias.

The groups are defined as follows:

- Intent-to Treat Population**

The Intent-to-Treat (ITT) Population is defined to be all enrolled subjects. An enrolled subject is a subject that has signed informed consent, all screening procedures have been successfully completed, is eligible and can receive treatment. The ITT population will not be analyzed for the annual reports and will only be included in the final report.

- **Per Protocol Population**

The PP Population is defined to be all subjects in the ITT Population with no major protocol violations. The protocol deviations that will exclude a subject are as follows:

- The subject does not receive the ReUnion RSA System
- The subject does not meet all eligibility criteria
- The subject has a protocol deviation that is considered likely to affect subject outcomes.

After the clinical investigation has been completed, a review of the data will be conducted to determine which subjects are to be excluded from the PP population.

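### Protocol 9.3 lets an implanted subject be withdrawn from follow-up for a late-noted eligibility violation or for non-compliance, with no threshold or decision-maker, which can informatively censor higher-risk subjects

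*Protocol*

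**What the plan says.** Protocol 9.3 ends with a paragraph that follows withdrawal reasons a to e. It opens: "A subject may also be withdrawn if the subject is non-compliant with the clinical investigation procedures or visits". It then extends the same permission to a subject "if a selection criteria violation is noted after the subject received the clinical investigation treatment", on the condition that "it is determined that the subject should be discontinued". The paragraph does not say how much non-compliance is enough, who decides, or on what criteria. On data it says: "All data collected up until the point of withdrawal will be included in the final analysis". Nothing provides for follow-up after that point. SAP 5.3 refers back to these procedures.

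Other parts of the plan bear on the same subjects:

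- Protocol 10.3, for a visit missed and out of window: "every effort should be made to collect data instead of noting the visit as missed". Notes b and d to the schedule of events repeat this and allow the ASES score to be taken by phone.
- Protocol 9.3 b, before a subject is called lost to follow-up: documented contact attempts, which "should include at least two attempts to contact the subject by phone and one attempt via a certified letter".
- Protocol 11.2 and SAP 5.1: subjects who do not meet all eligibility criteria are left out of the PP population, decided by data review after the study is complete. If exclusions occur: "In this occasion, there will be two groups being fully analyzed to ensure transparency and avoid bias". The ITT definition, however, describes an enrolled subject as one who is eligible.
- Protocol 11.3.3 and SAP 6.6 and 6.7.3: in the Kaplan-Meier analyses, subjects without an event are censored at their last or most recent visit. Device-related AEs and survivorship are to be assessed to 10 years.
- Protocol 11.4 and SAP 4.6: missing data are counted and reported. No sensitivity analysis is planned.

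**The concern.** The treatment is one operation. A late eligibility finding or poor attendance does not undo exposure to the implant, so ending data collection loses information about a device still in use.

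The loss may be related to outcome. Exclusion c concerns "bone stock compromised by disease, infection or prior implantation which cannot provide adequate support and/or fixation to the prosthesis", and exclusions b and e are likewise worded in terms of instability, fixation failure or failure of the device. A subject found after surgery to meet one of these is, by the protocol's own account, more likely to have an event. If follow-up stops, Kaplan-Meier censors that subject at the last visit and assumes the same later risk as those who remain. The study has no concurrent control, so no comparison arm would carry the same bias.

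At stake are the 10-year device-related AE and reoperation estimates and the completeness of the 24-month ASES data.

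**Working it through.** **1. The rules side by side**

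- *Missed visits.* 10.3 and note b say to collect the data late, and note d supplies a phone route for the primary endpoint. The last paragraph of 9.3 lets the same subject be withdrawn. No threshold separates the two.
- *Contact effort.* Loss to follow-up requires two phone attempts and one certified letter. Withdrawal for non-compliance requires none, although both can describe a subject who stops attending.
- *Eligibility violations.* 11.2 handles these by analysis set, decided at the end. Withdrawal under 9.3 acts during the study and removes data that no later choice of analysis set can restore.

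**2. The plan's own power figure**

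Inputs (Protocol 11.1): mean 71.27, SD 19.40, tested value 51.87, n = 10, two-sided alpha 0.05. Standardised effect = (71.27 - 51.87)/19.40 = 1.0. One-sample t-test power from the noncentral t with 9 df is 80.31%, against 80.3% stated. With 80 enrolled and the plan's 56% drop-out, 80 x 0.44 = 35.2 scores remain, and power exceeds 99.9%. The issue is bias and completeness, not power.

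**3. Effect on the 24-month ASES**

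Assumed, not in the documents: 4 to 8 of 80 subjects withdrawn under the clause, with a true mean 15 to 20 points below the others.

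- Shift in the mean over all 80 = (number withdrawn/80) x deficit. Low: (4/80) x 15 = 0.75 points. High: (8/80) x 20 = 2.0 points.
- SE with 35 scores = 19.40/sqrt(35) = 3.28. The planned mean lies 19.40/3.28 = 5.9 SE above 51.87. After a 2-point shift it lies 17.40/3.28 = 5.3 SE above.
- Expected scores lost, if these subjects would otherwise drop out at the plan's rate: 4 x 0.44 = 1.8 to 8 x 0.44 = 3.5 of 35.2, or 5% to 10%.

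**4. Effect on 10-year Kaplan-Meier failure**

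Assumed, not in the documents: constant hazards; 10% failure at 10 years in eligible subjects, so h0 = -ln(0.90)/10; a fraction f of violators with hazard HR x h0; all violators withdrawn at time w; no other loss.

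- True failure = 1 - [(1 - f) x 0.90 + f x 0.90^HR].
- Kaplan-Meier limit = 1 - [(1 - f) x exp(-h0 w) + f x exp(-HR h0 w)] x exp(-h0 (10 - w)).

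| f | HR | True | w = 6 weeks | w = 1 year | w = 2 years |
|---|---|---|---|---|---|
| 5% | 2 | 10.45% | 10.01% | 10.05% | 10.09% |
| 5% | 4 | 11.22% | 10.02% | 10.14% | 10.28% |
| 10% | 2 | 10.90% | 10.01% | 10.09% | 10.19% |
| 10% | 4 | 12.44% | 10.03% | 10.28% | 10.55% |
| 20% | 2 | 11.80% | 10.02% | 10.19% | 10.38% |
| 20% | 4 | 14.88% | 10.07% | 10.56% | 11.10% |

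The understatement runs from 10.45 - 10.09 = 0.4 to 14.88 - 10.07 = 4.8 percentage points. For 4 to 8 subjects (5% to 10% of 80) the upper end is 12.44 - 10.03 = 2.4 points. With HR = 1 there is no bias.

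**The case against.** The clause is discretionary, and for eligibility violations it needs a separate determination, so a violation alone does not remove anyone. Data up to withdrawal are kept. The documents give no rate of use. All of this stands and limits what can be said about size.

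A reader might infer that 9.3 flatly contradicts 10.3. The documents do not support that. 10.3 concerns a single visit outside its window, and one can try to collect late data and withdraw the subject only if non-compliance persists. The gap is the missing threshold, together with the absence of the contact steps required under 9.3 b.

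A reader might also infer that everyone withdrawn this way has a worse prognosis. The documents make that link for exclusions b, c and e. They do not make it for every selection criterion, and they say nothing about outcomes in poor attenders.

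Nor can it be assumed that 11.2 already keeps violators in ITT. The PP exclusion for eligibility makes sense only if violators can be in ITT, yet the ITT definition requires eligibility. Since PP excludes them anyway, continued follow-up alone would leave the PP mean unchanged for eligibility violators.

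Finally, SAP 5.3 tabulates withdrawals by site and visit and lists the reasons. That makes use of the clause visible but does not recover the missing outcomes.

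**Conclusion.** The point holds as a weakness in the design of follow-up. Protocol 9.3 permits avoidable and possibly informative loss of implanted subjects, without a threshold, a decision-maker or the contact effort required elsewhere.

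The main effect is on the 10-year device-related AE and reoperation curves. When the subjects withdrawn are at higher risk, failure is understated, which favours the device. The 0.4 to 4.8 percentage points above illustrate this under assumed failure rates, hazard ratios and frequencies; they do not predict it. The second effect is on the completeness of the 24-month ASES data.

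A reader might infer that the primary conclusion is at risk. It is unlikely to be: even the assumed 2-point shift leaves the planned mean more than 5 SE above 51.87. The change is worth making because it is cheap and outcomes not collected at the time may not be recoverable later.

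**What to change.** Separate exclusion from an analysis set from the end of data collection.

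1. Replace the last paragraph of Protocol 9.3 with wording such as: *An implanted subject is not withdrawn solely because of a selection-criteria violation or missed visits. The deviation is recorded and PP status is decided under 11.2. ASES (by phone if needed), device-related AE/incident and reoperation data continue to be collected unless 9.3 a, b, c, d or the first paragraph of e applies.* Keeping 9.3 c in the list avoids a clash with the existing provisions on device removal. The best-interest and IRB routes in e are untouched.
2. Amend the ITT definition in Protocol 11.2 and SAP 5.1 so that an implanted subject later found ineligible stays in ITT. Without this, the retained data may not enter either analysis set.

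The cost is a paragraph in 9.3, a sentence in each document for ITT, and a little extra phone follow-up for a few subjects. The change concerns data collection only. Some persistent non-attenders will still give no data and will then be handled as lost to follow-up under 9.3 b.
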